6.4. Study Restrictions

6.4.1. Contraception Restrictions

Male subjects with a female sexual partner of child-bearing potential must wear a condom (from first dosing until 3 months after final dosing) in addition to their female partner using a highly effective method of contraception, from first dosing until 3 months following final dosing. Contraceptive methods that can achieve a failure rate of less than 1% per year when

used consistently and correctly are considered as highly effective birth control methods. Such methods include:

- Combined (oestrogen and progestogen containing) hormonal contraception associated with inhibition of ovulation:
 - Oral
 - Intravaginal
 - Transdermal
- Progestogen-only hormonal contraception associated with inhibition of ovulation:
 - Oral
 - Injectable
 - Implantable
- Intrauterine device or intrauterine hormone-releasing system
- Bilateral tubal occlusion
- Surgical sterilisation

If the male subject is vasectomised then this will be accepted as a second form of highly effective contraception, in addition to the subject also wearing a condom. Sexual abstinence is considered a highly effective method only if defined as refraining from heterosexual intercourse during the entire period of risk associated with study treatment and must be part of the preferred and usual lifestyle of the subject.

6.4.2. Lifestyle Restrictions

Subjects should abstain from strenuous exercise for 48 hours prior to each blood collection for clinical laboratory tests, and while in the CRU.

Subjects participating in Part B of the study must refrain from sunbathing during their participation in the study (from Screening to discharge from the CRU following completion of all procedures).

6.4.3. Meals and Dietary Restrictions

The subjects are required to adhere to the following restrictions:

- Subjects should refrain from consumption any food or drinks containing cranberry, pomegranate, starfruit, grapefruit, pomelos, exotic citrus fruits, or Seville oranges (including marmalade and juices made from these fruits) within 14 days before admission and throughout the study until completion of study.
- Subjects should abstain from alcohol for 48 hours prior to each visit until after discharge from the CRU.
- Subjects should abstain from (methyl) xanthine- and caffeine-containing products for 48 hours prior to dosing until discharge from the unit from CRU.

- Subjects will be fasted overnight for at least 8 hours predose until 3 hours postdose. In addition, subjects should fast 4 hours prior to clinical laboratory evaluations at each visit. Water will be allowed ad libitum, except for 1 hour before and 3 hours after dosing. Standard meals and drinks will be provided at all other times.
- Subjects should refrain from consuming poppy seeds 48 hours prior to Screening and Day -1 (in each treatment period for Part A) to avoid a positive result on the drugs of abuse screen.

6.5. Subject Withdrawal Criteria

For all subjects withdrawn from the study, discontinuation procedures as described in [Appendix 1](#) and [Appendix 2](#) should be conducted prior to discharge in the study. In Part B, subjects will be replaced should they vomit after receiving their dose of IMP, or if they do not receive the ID capsaicin.

Reasons for withdrawal or discontinuation at any time during the study may include any of the following reasons:

- Adverse event: Clinical or para-clinical events occurred that, in the medical judgement of the Investigator for the best interest of the subjects, are grounds for discontinuation. This includes serious and non-serious AEs regardless of relation to the study medication.
- Withdrawal of consent: The subject desired to withdraw from further participation in the study in the absence of an Investigator determined medical need to withdraw. If the subject gave a reason for withdrawing it should be recorded in the eCRF.
- Investigator decision.
- Lost to follow-up: The subject stopped coming for visits and study personnel were unable to contact the subject.
- The subject tests positive for SARS-CoV-2 at any point during the study.
- Other: The subject was discontinued for a reason other than those listed above, such as termination of the study by the Sponsor. The reason(s) should be recorded in the eCRF.

6.6. Follow-up Procedures

The Investigator will make diligent attempts to contact subjects who fail to return for a scheduled visit or were otherwise unable to attend the follow-up visit. All discontinuations and the reason for early discontinuation will be documented by the Investigator, and if appropriate on the AE form.

7. SAFETY ASSESSMENTS

Baseline safety data assessments for all parts of the study will be collected predose at the nearest timepoint to dosing as shown in [Appendix 1](#) and [Appendix 2](#). The subjects will attend a follow-up visit 5 to 7 days post-discharge from the CRU for safety follow-up procedures as shown in the Schedule of Assessments ([Appendix 1](#) and [Appendix 2](#)).

7.1. Clinical Laboratory Evaluations

Clinical laboratory evaluations will be performed including [clinical chemistry, haematology, coagulation, and urinalysis] as indicated in the table below ([Table 4](#)). Serology, drugs of abuse, alcohol and SARS-CoV-2 (according to the current UK standard testing) screen will be performed as indicated in the table below ([Table 4](#)). Approximate blood sampling volumes are provided in [Appendix 3](#).

All blood and urine analyses will be conducted at the sampling times indicated in the Schedule of Assessments ([Appendix 1](#) and [Appendix 2](#)). The clinical laboratory evaluation results will be collected at screening (in Part A and B) and at check-in on Day -1 to the CRU (in Part B), in time for results to be reviewed prior to dose administration. For abnormal values, additional testing may be performed, or clinical laboratory evaluations may be added to evaluate the abnormal values. Clinically significant values should be followed until resolution or until they reach a stable state.

Table 4: Clinical Laboratory Evaluations

Blood Chemistry Amylase BUN Creatinine Glucose Sodium Potassium Phosphate Chloride Calcium AST ALT GGT Alkaline phosphatase Total bilirubin Uric acid Albumin Total protein Lactate dehydrogenase	Urinalysis (dipstick) Glucose Bilirubin Ketone Specific Gravity Blood pH Protein Urobilinogen Nitrite Leukocyte Esterase Microscopic analysis if dipstick is abnormal
Haematology Haemoglobin Haematocrit RBC count RBC indices (MCV, MCH, MCHC) Platelet count White blood cell count with differential	Drugs of abuse Amphetamines Barbiturates Benzodiazepines Cocaine Cannabinoids Opiates
Coagulation Prothrombin time International normalization ratio Activated partial thromboplastin time	Other Screens Alcohol (breath) SARS-CoV-2 according to the current UK standard testing

	Virology Anti-HIV I/II Anti-HCV HBsAg
--	---

Abbreviations: ALT – alanine aminotransferase; Anti-HIV I/II – Anti-human immunodeficiency virus I and II; Anti-HCV – anti-hepatitis C antibody; AST: aspartate aminotransferase; BUN – blood urea nitrogen; GGT – gamma-glutamyltransferase; HBsAG – hepatitis B surface antigen; MCV – mean corpuscular volume; MCH - mean corpuscular haemoglobin; MCHC – mean corpuscular haemoglobin concentration; SARS-CoV-2 – severe acute respiratory syndrome coronavirus 2.

7.2. 12-lead Electrocardiogram

A 12-lead ECG will be collected at the timepoints indicated in the Schedule of Assessments ([Appendix 1](#) and [Appendix 2](#)). The 12-lead ECG will be collected in triplicate, approximately 1 minute apart, at Screening, and within approximately 1-hour predose. Single readings will be collected at all other timepoints. 12-lead ECGs should be obtained after the subject has rested in the supine position for at least 5 minutes. In the event of an abnormal finding, recordings should be performed in triplicate. Triplicate recordings will be performed within 30 minutes of an abnormal finding. The ECG machine used should automatically calculate the HR and PR, RR, QRS and QTcF intervals.

For timepoints with multiple assessments:

- collect the ECG first,
- then vital signs,
- then the PK blood draw. The PK sample should be collected at the scheduled time postdose.

7.3. Vital Signs and Oral Temperature

Supine vital signs, including heart rate, blood pressure and oral temperature will be collected at the timepoints in the Schedule of Assessments ([Appendix 1](#) and [Appendix 2](#)). Predose vital signs should be collected within 30 minutes predose.

For timepoints with multiple assessments:

- collect the ECG first,
- then vital signs,
- then the PK blood draw. The PK sample should be collected at the scheduled time postdose.

7.4. Physical Examinations

A physical examination, including height, BMI, and body weight, and assessments of the head, eyes, ears, nose, throat, skin, thyroid, neurological, lungs, cardiovascular system, abdomen (liver and spleen), lymph nodes and extremities will be conducted at the times indicated in the Schedule of Assessments ([Appendix 1](#) and [Appendix 2](#)).

7.5. Adverse Event Reporting

Adverse event monitoring will be conducted at the times specified in the Schedule of Assessments ([Appendix 1](#) and [Appendix 2](#)). Adverse events will be elicited through non-

leading questions and spontaneous reporting by subjects. The Investigator is responsible for evaluating AEs and for the appropriate medical care of subjects during the study.

7.5.1. Definition and Criteria

7.5.1.1. Adverse Event

An AE is any untoward medical occurrence in a study subject which either emerges, or worsens from Screening, during the clinical study, regardless of its potential relationship to the medicinal product. An AE, therefore, can be any unfavourable or unintended sign, including a clinically-significant abnormal laboratory finding, symptom, or disease temporally associated with the use of a medical product, whether or not it is considered to be study medication related.

Examples of an AE include:

- Exacerbation of a pre-existing condition including either an increase in frequency and/or intensity of the condition.
- New conditions detected or diagnosed.
- Signs or symptoms of a drug interaction.
- Signs or symptoms of a suspected overdose of either IMP or a concurrent medication (overdose per se should not be reported as an AE/SAE)
- A new laboratory abnormality occurring after the start of the study (i.e., after Screening) that results in subject withdrawal from the study or medical treatment or further follow-up.
 - Note: abnormal laboratory or other values obtained during Screening that preclude a subject from entering the study are not considered AEs but will be recorded.

Adverse events may include pre- or post-treatment events that occur as a result of Protocol-mandated procedures (i.e., invasive procedures, modification of subject's previous therapeutic regimen).

A medical intervention to address an AE is an “action taken” and not an AE itself.

7.5.1.2. Serious Adverse Event

An SAE is any untoward medical occurrence that, at any dose:

- Results in death,
- Is life-threatening,
 - Note: The term ‘life-threatening’ in the definition of ‘serious’ refers to an event in which the subject was at risk of death at the time of the event. It does not refer to an event, which hypothetically might have caused death, if it were more severe.
- Requires hospitalisation or prolongation of existing hospitalisation,
 - Note: In general, hospitalisation signifies that the subject has been detained (usually involving at least an overnight stay) at the hospital or emergency ward for observation and/or treatment that would not have been appropriate in the

physician's office or out setting. Complications that occur during hospitalisation are AEs. If complication prolongs hospitalisation or fulfils any other serious criteria, the event is serious. When in doubt whether 'hospitalisation' occurred or was necessary, the AE should be considered serious.

- Results in persistent or significant disability or incapacity,
 - Note: The term 'disability' means a substantial disruption of a person's ability to conduct normal life functions. This definition is not intended to include experiences of relatively minor medical significance such as uncomplicated headache, nausea, vomiting, diarrhoea, influenza and accidental trauma (e.g., sprained ankle) which may interfere or prevent everyday life functions but do not constitute a substantial disruption.
- Is a congenital abnormality or birth defect,
- Is an important medical event.
 - Note: Medical or scientific judgement should be exercised in deciding whether reporting is appropriate in other situations, such as important medical events that may not be immediately life threatening, or result in death or hospitalisation, but may jeopardise the subject or may require medical or surgical intervention to prevent one of the other outcomes listed in the above definition. These should also be considered serious. Examples of such events are invasive or malignant cancers, intensive treatment in an emergency room or at home for allergic bronchospasm, blood dyscrasias or convulsions that do not result in hospitalisation, or development of drug dependency or drug abuse.
 - Note: The terms "serious" and "severe" ARE NOT synonymous. The term "severe" is often used to describe the intensity (severity) of a specific event (as in mild, moderate or severe myocardial infarction); the event itself, however, may be of relatively minor medical significance (such as severe headache). This is NOT the same as "serious", which is based on subject/event outcome or action criteria described above and are usually associated with events that pose a threat to a subject's life or functioning. A severe AE does not necessarily need to be considered serious. For example, persistent nausea of several hours duration may be considered severe nausea but not an SAE. On the other hand, a stroke resulting in only a minor degree of disability may be considered mild but would be defined as an SAE based on the above criteria. Seriousness (not severity) serves as a guide for defining regulatory reporting obligations.

7.5.1.3. Suspected Unexpected Serious Adverse Reactions (SUSARs)

A SUSAR is defined as an AE that occurs in a clinical trial subject, which is assessed by the Sponsor and or study Investigator as being unexpected, serious and as having a reasonable possibility of a causal relationship with the study drug. The Sponsor is responsible for the regulatory reporting of SUSARs. An AE will be considered unexpected if the nature, severity, frequency of the event is not consistent with the risk information previously described for the IMPs, and reported in the IB for the study product KLS-GABA (Reference Safety Information [RSI] Section) or in the SmPCs for the medicinal product KLS and gabapentin (Neurontin 300 mg hard capsules), respectively. The process for recording and reporting SUSARs is defined in the Sponsor SOPs in accordance with regulatory guidelines.

7.5.1.4. Expectedness

An AE is considered expected if it is either listed in the IB for KLS-GABA (RSI Section) or the SmPCs for KLS and gabapentin (Neurontin 300 mg hard capsules). An event is unexpected when it is not listed in the IB for KLS-GABA or the SmPCs for KLS and gabapentin (Neurontin 300 mg hard capsules), including when it is not listed at the specificity or severity that has been observed and reported in the IB or SmPCs. Events that are mentioned in the IB or SmPCs as occurring with a class of drugs, or as anticipated from the pharmacological properties of the drug but are not specifically mentioned as occurring with the particular IMP, are considered unexpected.

The determination of expectedness shall be made by the Sponsor on the basis of the IB for KLS-GABA RSI Section, or the SmPC for KLS or gabapentin (Neurontin 300 mg hard capsules).

7.5.1.5. Clinical Laboratory Abnormalities and Other Abnormal Assessments as Adverse Events and Serious Adverse Events

Abnormal laboratory findings (e.g., clinical chemistry and haematology) or other abnormal assessments (e.g., ECGs, vital signs) that are judged by the Investigator as clinically significant will be recorded as AEs or SAEs if they meet the definition of an AE or SAE. Clinically significant abnormal laboratory findings or other abnormal assessments that are detected during the study or are present at baseline and significantly worsen following the start of the study will be reported as AEs or SAEs. The Investigator will exercise his or her medical and scientific judgment in deciding whether an abnormal laboratory finding, or other abnormal assessment is clinically significant. Liver chemistry thresholds have been designed to assure subject safety. When subjects meet the hepatic transaminase threshold criteria (AST or ALT $\geq 3 \times$ ULN), the subject should undergo close observation, including monitoring for symptoms (clinical symptoms of hepatitis, or hypersensitivity, fatigue, decreased appetite, nausea, vomiting, abdominal pain, jaundice, fever, or rash) and hepatic function (AST, ALT, alkaline phosphatase [ALP]), and fractionated bilirubin at least every 48 hours, until symptoms and/or hepatic function abnormalities resolve, stabilise, or return to baseline values. This event should be reported to Dompé within 24 hours of learning of its occurrence. [Appendix 4](#) represents the decision tree for whether or not study medication will be discontinued. A specialist or hepatology consultation should be considered in cases of protocol-mandated study medication discontinuation.

In addition, every attempt should be made to obtain the following for any subject who meets the hepatic transaminase threshold criteria:

- Viral hepatitis including: hepatitis A immunoglobulin (IgM) antibody, hepatitis B surface antigen and hepatitis B core antibody (IgM), HCV RNA, cytomegalovirus IgM antibody, Epstein-Barr viral capsid antigen IgM antibody (or if unavailable, obtain heterophil antibody or monospot testing), and hepatitis E antibody (if subject resides outside UK or has travelled outside UK in past 3 months).
- Serum creatine phosphokinase and lactate dehydrogenase. Record the appearance or worsening of clinical symptoms of hepatitis, or hypersensitivity, fatigue, decreased appetite, nausea, vomiting, abdominal pain, jaundice, fever, or rash as relevant on the AE report form.

- Record use of concomitant medications, including paracetamol, herbal remedies, other OTC medications, putative hepatotoxins, or alcohol on the concomitant medications report form.
- The following are required for subjects with AST or ALT $\geq 3 \times$ ULN and bilirubin $\geq 2 \times$ ULN, but are optional for other abnormal liver chemistries:
 - Anti-nuclear antibody, anti-smooth muscle antibody, and type 1 anti-liver kidney microsomal antibodies.
 - Liver imaging (ultrasound, magnetic resonance, or computerized tomography) to evaluate liver disease.

7.5.1.6. Pharmacokinetic Sampling Associated with Serious Adverse Events or Severe Adverse Events

Every possible attempt will be made to collect an unscheduled PK sample if a subject experiences an SAE or a severe AE. As the determination of an SAE or a severe AE is sometimes retrospective, unscheduled PK samples obtained when an event that is suspected to be serious or severe are also permitted.

7.5.2. Evaluating Adverse Events and Serious Adverse Events

All AEs will be assessed on two descriptive parameters: intensity and relationship to the study medication:

- Intensity refers to the severity of an event and references impact on a subject's functioning.
- Relationship refers to the likelihood that the event being assessed was caused by the study medication.

The intensity of each AE (including SAEs) will be recorded in the eCRF and assigned to one of the following categories:

- **Mild:** An event that is easily tolerated by the patient, causing minimal discomfort and not interfering with everyday activities.
- **Moderate:** An event that is sufficiently discomforting to interfere with normal everyday activities.
- **Severe:** An event that prevents normal everyday activities.

For AEs and SAEs, the relationship to the study treatment is to be assessed according to the following definitions:

Not related: There is no reasonable association between the study treatment and the suspected event.

Unlikely related: It is doubtful that there is an association between the study treatment and the suspected event. The event could have been produced by the subject's clinical state or other modes of therapy administered to the subject.

Possibly related: The suspected adverse event may or may not follow a reasonable temporal sequence from study drug administration. The event could have been produced or mimicked

by the subject's clinical state or by other modes of therapy concomitantly administered to the subject.

Probably related: The suspected adverse event follows a reasonable temporal sequence from study treatment administration, abates upon discontinuation of the treatment; and cannot be reasonably explained by the known characteristics of the subject's clinical state.

Definitely related: The suspected adverse event has a strong relationship with study treatment administration, the event abates upon discontinuation of treatment and, if applicable, re-appears upon repeat exposure.

When assessing the relationship to the study medication, the following criteria will be considered:

- Known class effect
- Biological plausibility
- Lack of alternative explanation – concomitant drug or disease

7.5.3. Reporting Procedures and Requirements

7.5.3.1. Adverse Events

Events occurring from the time of signed informed consent will be considered as AEs. A baseline AE assessment will occur after Screening. All AEs between screening to the follow-up visit will be recorded in source and eCRF, whether or not considered study medication related. All AEs that are possibly or probably related to study medication will be followed until resolution or database lock, whichever occurs first. Also, the sign, symptom, or disease present before the baseline AE assessment are only considered AEs if they worsen after this point. Any AEs already documented at a previous assessment and designated as ongoing should be reviewed at subsequent visits as necessary. If these have resolved, this should be documented. Changes in intensity or frequency of AEs should be recorded as separate events (i.e., a new record started). The Investigator should report all AEs on the AE page(s) of the eCRF and source documents, regardless of seriousness, severity, and causality. Whenever possible, an AE will be reported using a diagnostic term, (e.g., "common cold" or "upper respiratory infection" rather than "runny nose, cough, mild fever") and should be described with the attributes described in [Section 7.5.1.1](#).

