5. ANALYSIS PERIODS

There will be two treatment periods within Part A. Analysis phases and treatment periods:

- SCREENING analysis phase starts with sign of Informed Consent and ends with first IMP administration;
- TREATMENT PERIOD 1 analysis phase/period starts with first IMP administration within Part A and ends with second IMP administration within Part A;
- TREATMENT PERIOD 2 analysis phase/period starts with second IMP administration within Part A and ends with the end of study.

There will be one treatment period within Part B. Analysis phases and treatment periods:

- SCREENING analysis phase starts with sign of Informed Consent and ends with first IMP administration;
- TREATMENT PERIOD analysis phase/period starts first study drug administration and ends with the end of study.

Statistical Analysis Plan

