6.6.1. Adverse Events (AE)

All verbatim AE terms will be coded using MedDRA of latest version (version will be clarified in the output footnotes) and summarized by system organ class (SOC) and preferred term (PT).

A TEAE will be defined as any AE that has an onset on or after taking study drug, or any pre-existing condition that has worsened on or after taking study drug. For Part A each TEAE will be attributed to treatment period and treatment according to onset date.

The frequency and incidence of TEAEs will be summarised by SOC and PT by treatment according to treatment period and overall. Summaries will also include, but not limited to, relationship to study drug and maximum severity. The summary will be sorted by SOC and PT by frequency from the highest to the lowest. All AE data will be listed.

For each of the summaries produced at the participant level, multiple occurrences of the same event within a participant will be counted once in the summaries by SOC and PT; multiple occurrences of the same event within a participant will be counted once in the maximum severity category and/or maximum drug relationship category. If severity or relationship is found to be missing, the most severe occurrence will be imputed for that particular summary.

These summaries will also present the number of events that occurred, so multiple occurrences of the same event within a participant will all be accounted for in the maximum intensity category and maximum relationship category they were classed as.

6.6.2. 12-lead electrocardiogram (ECG)

Descriptive statistics will be calculated for absolute value and change from baseline (pre-dose) of each parameter by visit and by treatment according to treatment period and overall. Where multiple values are recorded at a timepoint for a subject, the mean of the values will be used in the summary statistics.

Statistical Analysis Plan

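### Split adverse event records are never linked, so one episode is counted as several events and, less often, an improvement can become a treatment-emergent event

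*Protocol*

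**What the plan says.** **Recording (Protocol 7.5.3.1).** "Changes in intensity or frequency of AEs should be recorded as separate events (i.e., a new record started"). The rule is not limited to worsening. Collection begins at consent: "Events occurring from the time of signed informed consent will be considered as AEs". One restriction follows: "the sign, symptom, or disease present before the baseline AE assessment are only considered AEs if they worsen after this point". The section times the baseline AE assessment only as coming after Screening. Protocol Section 7 takes baseline safety data before dosing, at the timepoint closest to it.

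**Classification (SAP 6.6.1).** "A TEAE will be defined as any AE that has an onset on or after taking study drug, or any pre-existing condition that has worsened". Such worsening must likewise date from dosing or later. The two limbs are joined by *or*.

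**Attribution (SAP 6.6.1 and 5).** "For Part A each TEAE will be attributed to treatment period and treatment according to onset date". The boundary is the second dose: "TREATMENT PERIOD 2 analysis phase/period starts with second IMP administration within Part A and ends with the end of study".

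**Counting (SAP 6.6.1).** Participant-level summaries count repeats of an event once per SOC and PT, and once at the highest severity or relationship. The next paragraph adds event counts: "These summaries will also present the number of events that occurred, so multiple occurrences of the same event within a participant will all be accounted" ... The protocol synopsis also promises both the number of AEs and their incidence.

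Neither document gives the records of one episode a common identifier, says which start date a split record carries, or sets aside records opened because an event improved.

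**The concern.** The recording rule and the analysis rules are each workable alone. Together they let the unit of recording (a spell at constant intensity and frequency) stand in for the unit of interest (an episode). A second record opened after dosing can meet the onset limb of the TEAE definition by itself, so the worsening limb never screens it. The SAP evidently wants pre-existing conditions to count only if they get worse; the splitting rule can defeat that.

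Safety and tolerability is the Part A secondary objective and is among the secondary objectives of Part B, and AEs are summarised by treatment. At stake are the number of events reported per treatment, which rises most for AEs that fluctuate, and occasionally whether a subject is counted under a treatment at all.

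**Working it through.** The plan gives no figure to reproduce; this is a check of what the rules do when applied as written.

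**Inputs.** Part A: 12 subjects, two-period crossover, washout of at least 7 days (Protocol 3.1). Part B: 128 subjects split evenly over 8 treatments (Protocol 3.2). Rules: as set out above.

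**1. Event count.** With k changes of intensity or frequency, an episode produces k + 1 records. A headache that begins after dosing and goes mild, moderate, mild has k = 2, so 2 + 1 = 3 events. The participant count is still 1, at moderate. Counted by episode, it is 1 event. For an episode that begins after dosing and stays within one treatment period, the inflation does not depend on which start date the later records carry: either date falls after that dose.

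**2. TEAE status and treatment.** Here I assume that a split record carries the date of the change. Dose 1 is day 0 and dose 2 is day 7, an illustrative shortest gap; a longer gap does not alter the classification. Four hours is 4/24 = 0.17 day.

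| History | Record onsets (days) | Each record by its own onset | Episode by first onset |
|---|---|---|---|
| Moderate before dose 1 (after the baseline AE assessment), mild 4 h after dose 1 | -0.5; 0.17 | Not a TEAE; TEAE on Period 1 drug | No TEAE |
| Moderate 1 day after dose 1, still present at dose 2, mild 4 h after dose 2 | 1; 7.17 | TEAE on Period 1 drug; TEAE on Period 2 drug | Period 1 drug only |

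In both histories the only change after the later dose is an improvement.

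**3. What the existing safeguards reach.**

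- The once-per-participant rule removes duplicates within a treatment. It does not make a pre-dose event non-emergent, does not work across the two Part A treatments, and leaves event counts untouched.
- The worsening-only rule removes conditions present before the baseline AE assessment. It does not reach an AE arising between that assessment and dosing, and nothing says it restarts before dose 2.

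**4. Size per affected subject.** Part A: 1/12 = 8.3 percentage points, if all 12 receive both treatments. Part B: 128/8 = 16 per arm, so 1/16 = 6.25 percentage points.

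**The case against.** The strongest reply is that the plan already contains most of the protection. If the baseline AE assessment is the predose check, as Protocol Section 7 suggests and as both schedules allow by listing AE monitoring at predose, the worsening-only rule covers nearly everything present at dosing and the first history almost disappears. The once-per-participant rule keeps incidence and maximum severity correct within a treatment. The second history needs an AE that follows a single dose, survives at least 7 days of washout and then eases after dose 2, which should be uncommon. The separate worsening limb shows what the SAP intends. The safety analysis is descriptive, with no hypothesis testing (SAP Section 3), and all AEs are listed, so episodes could be traced by hand. The eCRF, the Data Management Plan or the table shells, none of which is available here, may settle the start date or the linkage.

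Most of this stands and limits the size of the point. It does not remove the event-count effect, which arises for any fluctuating AE in either part. Nor does the evident intent decide the classification, because the onset limb is sufficient by itself. The timing of the baseline AE assessment is not fixed in 7.5.3.1.

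A reader might also infer that Part B is exposed by design, because every subject receives capsaicin on Day -1 and would carry resolving events into Day 1. The documents do not support that. Protocol 3.3 puts the induced symptoms at up to 8 hours. Appendix 2 places the Day -1 injection at a similar time of day to the Day 1 injection, which is given at t_max after dosing. The gap from the Day -1 injection to dosing is therefore about 24 h minus t_max, and it falls below 8 h only if t_max exceeds 24 - 8 = 16 h. Pain, hyperalgesia, allodynia and flare are also collected as pharmacodynamic measurements, and nothing says they are routinely entered as AEs.

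**Conclusion.** The point holds in a limited form. Applied as written, the two documents inflate the number of events: k + 1 for an episode with k changes, assuming each record is counted as an occurrence. Participant counts by SOC and PT, and by maximum severity, are protected within a treatment.

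Two rarer effects rest on the further assumption that a split record carries the date of the change. That is the natural reading of a separate event with a new record, but it is not stated. An AE arising after the baseline AE assessment and easing after dosing becomes a TEAE. A Part A Period 1 AE that outlasts the washout and eases after dose 2 is credited to both drugs. Each affected subject is worth 8.3 percentage points in Part A or, for the first effect, 6.25 in a Part B arm. These are sizes per subject, not expected biases; no frequency can be derived from the documents. The inference that false TEAEs will be common, or will distort incidence generally, is not supported.

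**What to change.** - **Protocol 7.5.3.1 or the eCRF completion guideline:** give the split records of one episode a common identifier, and state which start date each record carries. State that the baseline AE assessment is made predose, consistent with Section 7.
- **SAP 6.6.1, classification:** set TEAE status and Part A treatment from the first onset of the episode, or from the first worsening above the pre-dose level of that period. State that a record opened for an improvement never creates a TEAE.
- **SAP 6.6.1, counting:** in the event counts, count each episode once per treatment period, at its maximum intensity in that period.

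The cost is one eCRF link field or completion guideline, the SAP wording, and a small derivation step. It should be settled before database lock.
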